1.2 Study Description

This is a prospective, randomized, controlled, multicenter, interventional study performed in two phases, as stated below. Up to 150 eyes meeting subject eligibility criteria listed in Section 6 of the protocol will be randomized to study treatment at up to 10 investigational sites.

Note, only one eye per subject may be treated under the study protocol. If both eyes qualify for the study, the study investigator will choose which eye will be the study eye. Unless specified otherwise, ocular results refer to the study eye only. Therefore, throughout this SAP and corresponding tables and data listings, the number of subjects and eyes are synonymous.

Dose Selection Phase: During this phase, the first cohort (Cohort 1) of 63 subjects was randomized (1:1:1) to receive either a CyPass Micro-Stent with 30 μl adjunct Healon 5 viscoelastic, a CyPass Micro-Stent with 60 μl of adjunct Healon 5 viscoelastic, or a CyPass Micro-Stent without adjunct viscoelastic. After completion of at least 3 months follow-up on all subjects in this phase, an interim review of safety and efficacy data was performed to determine the optimum dose of adjunct viscoelastic for the study expansion phase.

Expansion Phase: After the dose selection phase, the study was expanded to include a second cohort (Cohort 2) of up to 90 additional subjects who were randomized 1:1 to either the CyPass Micro-Stent without adjunct viscoelastic or to the CyPass Micro-Stent with 60 μ l adjunct viscoelastic (the dose selected based on Dose Selection Phase results).

Visit Schedule and Visit Windows: Enrolled study subjects are expected to participate in the study from Screening/Baseline through 12 months postoperatively in accordance with Table 1 – Study Examinations and Procedures (Appendix 1 in the study protocol) below.

Note, prior to protocol version D, Amendment dated 07Oct2014, the 12 Month Washout visit was not required for mainly the initial dose selection phase subjects who were on IOP lowering medication. All Cohort 2 patients were enrolled under protocol version D or a later version.

Version: 2.0; Most-Recent; Effective; CURRENT

Status: Effective

Document: TDOC-0053376 Version: 2.0; Most-Recent; Effective; CURRENT

Status: Effective

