3.1 General Reporting Conventions

- Only one eye per subject may be treated under the study protocol. If both eyes qualify
 for the study, the study investigator will choose which eye will be the study eye.
 Unless specified otherwise, all ocular results refer to the study eye only. Therefore,
 throughout this SAP and corresponding tables and data listings, the number of
 subjects and eyes are synonymous.
- Available data at each assessment time point will be presented. No imputations will be made for missing data.

Document: TDOC-0053376 Version: 2.0; Most-Recent; Effective; CURRENT

Status: Effective

- Appropriate descriptive statistics will be computed and displayed by assessment time point for both continuous and categorical variables. For continuous variables, descriptive statistics include n (number of subjects/eyes) with non-missing data, mean, standard deviation (SD), median, minimum and maximum values. For categorical parameters, the number and percentage of subjects/eyes within each category will be presented. The denominator for percentages will be based on the number of subjects with non-missing data appropriate for summary purposes. Unless otherwise noted, percentages will be presented to one decimal place. Any confidence intervals (CI) will be at the alpha = 0.05 (two-sided) level.
- Summary tables will be presented by treatment and overall, as appropriate, for both phases/cohorts combined.
- Study day: Study day will be calculated relative to the date of stent implantation surgery (Day 0) as: Date of event – date of surgery. This formula will be used when calculating days to a specific event (i.e., ocular medications and/or AE start date). A negative study day indicates an event prior to surgery.
- Individual data listings of select data represented on the eCRF will be provided to facilitate investigation of the tabulated values and to allow for clinical review of key variables. All data listings will be sorted by Treatment (i.e., CyPass, CyPass with 30 μl, and CyPass with 60 μl), Cohort (1 or 2), site-subject number, visit, and assessment time points where appropriate. Data from unscheduled visits will be excluded from the summary tables (except for adverse events) but included, chronologically, in the data listings.
- Analyses will be generated using SAS® version 9.2 or higher.

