3.2 Baseline References

For reporting IOP results relative to ocular hypotensive medication use, two baseline references will be used as follows:

Document: TDOC-0053376 Version: 2.0; Most-Recent; Effective; CURRENT

Status: Effective

Baseline1 = The pre-surgery assessments obtained at the scheduled Screening visit
that are prior to washout (if necessary) for enrolled subjects regardless of whether the
subject is taking any ocular hypotensive medications. Also referred to as 'Medicated'
or 'Regardless of medications'.

• Baseline2 = The pre-surgery assessments obtained at the scheduled Baseline visit that are after washout of subject's ocular hypotensive medications for those subjects taking hypotensive medications; if a subject is not medicated at Screening, then Baseline2 = Baseline1 (i.e., per protocol Section 7.1, "Subjects who are medication naïve at screening may have the screening and baseline testing performed on the same day."). Also referred to as 'Unmedicated' or 'Without medications'.

All other data will reference only one baseline, designated "Baseline", defined as the last assessments obtained prior to CyPass implantation surgery on Day 0.

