5.1 Efficacy Endpoints

Primary Efficacy Endpoint

The outcome of \geq 20% decrease in IOP from baseline (unmedicated/Baseline2) up to 12 months post-operatively without IOP lowering medications (IOP response) is determined as follows,

Percent change in IOP from baseline is defined as, for each subject,

$$Percent \ Change = \frac{PostOperative \ IOP - Baseline \ IOP}{Baseline \ IOP} \ge 100$$

such that negative percent changes represent a favorable effect, while positive percent changes represent an unfavorable effect. Therefore, IOP response is achieved if the percent change is $\geq 20\%$ lower than baseline (i.e. the percentage change is $\leq -20\%$).

 IOP response rate: Proportion of eyes meeting the effectiveness outcome is defined as the number of eyes with occurrence of ≥ 20% decrease from baseline divided by the number of eyes having non-missing post-Baseline and Baseline IOP measurements at each the given visit.

While the IOP response rate at 12 months without IOP lowering medications is the primary endpoint, results will be summarized at each postoperative visit relative to unmedicated baseline. Note, at 12 months for subjects being treated with ocular hypotensive medications, a washout for the 12 month assessment was intended to obtain unmedicated IOP measurements. Note: prior to version D of the protocol, the 12 Month Washout visit was not required for the initial dose selection phase subjects who were on IOP lowering medication

Document: TDOC-0053376 Version: 2.0; Most-Recent; Effective; CURRENT

Status: Effective

Secondary Efficacy Endpoints

[figure not shown]
 Rate of intraoperative and post-operative device related ocular adverse events up to 12 months postoperatively

```
Rate = \frac{\text{\# of subjects who experience } either \text{ an intraoperative } and/or \text{ post} - \text{operative device related ocular AE}}{\text{\# of subjects}}
```

such that device related includes definitely, probably, or possibly.

- Mean change in medicated IOP from baseline (Baseline1) to 12 months postoperatively regardless of medications
 - Computed for subjects having both non-missing baseline medicated IOP and
 12 month postoperative regardless of medications measurements.
- Proportion of eyes using ocular hypotensive medications at 12 months postoperatively

```

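### The visible primary-endpoint rule in SAP 5.1 does not say how to score an eye that is on IOP-lowering medication with no washed-out IOP

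*SAP*

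**What the plan says.** SAP 5.1 defines IOP response as a fall of at least 20% from the unmedicated baseline (Baseline2 in SAP 3.2), achieved off pressure-lowering drugs. SAP 5.3 repeats that condition. The formula for the rate does not. Its numerator is eyes with the required decrease, and its denominator is the "number of eyes having non-missing post-Baseline and Baseline IOP measurements at each the given visit".

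For medicated eyes, SAP 5.1 notes that "a washout for the 12 month assessment was intended to obtain unmedicated IOP measurements". SAP 1.2 says that before protocol version D "the 12 Month Washout visit was not required for mainly the initial dose selection phase subjects who were on IOP lowering medication", and that "All Cohort 2 patients were enrolled under protocol version D or a later version". Response is not only a Month 12 summary, because "results will be summarized at each postoperative visit relative to unmedicated baseline". The visit schedule in Protocol 2.6 has a washout visit only at Month 12.

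Two general conventions in SAP 3.1 also bear on this: "No imputations will be made for missing data", and "Summary tables will be presented by treatment and overall, as appropriate, for both phases/cohorts combined".

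**The concern.** The endpoint has two conditions, a sufficient fall in pressure and no medication. The visible computing rule carries only the first. The missing condition matters for an eye that is on medication at the visit and has no washed-out pressure, and the SAP's own text shows that such eyes can exist: washout was not required for some and only intended for the rest.

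Three treatments of such an eye fit the visible text:

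1. **Dropped.** It has no unmedicated value, nothing may be imputed, and so it leaves numerator and denominator.
2. **Scored on its on-drug IOP.** The formula taken alone asks only for a non-missing value.
3. **Kept as a failure.** The endpoint's label requires response off medication.

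Two programmers could thus report different primary rates from the same data. The first two treatments can raise an arm's rate above the share of eyes shown to have responded off drug.

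**Working it through.** **Reading the passages together.** At Month 12, treatment 1 fits best. The baseline is the unmedicated one, the washout exists to supply a matching unmedicated value, and SAP 6.3.4 lists the 12-month and the 12-month unmedicated assessments separately. At earlier visits no washout is scheduled, so a medicated eye has only an on-drug value, and treatment 2 becomes more likely.

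**Planned figure.** SAP Section 7 gives 30% against 60%, 43 eyes per arm, two-sided 0.05, likelihood ratio chi-square test, 80% power. This reproduces: 80.5% at 43 per arm and 79.6% at 42. The issue here is one of definition, and no stated figure is wrong because of it.

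**Where the eyes can come from.** SAP 1.2 gives 63 subjects in Cohort 1, randomized 1:1:1. An even split (assumed) gives 63/3 = 21 per arm, or 42 in the two compared arms. Only those on medication at Month 12 without a washout are affected.

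**Illustration of dropping.** Take whole eyes near the planned rates, with affected eyes counted as failures: 13/43 = 30.2% control and 26/43 = 60.5% visco-assisted, a gap of 30.2 points. Hold responders fixed and remove d affected eyes, so that rate = responders/(43 − d). The documents do not give d; the values below are assumptions.

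| Dropped, control / visco | Control | Visco | Gap (points) |
|---|---|---|---|
| 0 / 0 | 13/43 = 30.2% | 26/43 = 60.5% | 30.2 |
| 3 / 3 | 13/40 = 32.5% | 26/40 = 65.0% | 32.5 |
| 5 / 5 | 13/38 = 34.2% | 26/38 = 68.4% | 34.2 |
| 8 / 8 | 13/35 = 37.1% | 26/35 = 74.3% | 37.1 |
| 5 / 0 | 34.2% | 60.5% | 26.3 |
| 0 / 5 | 30.2% | 68.4% | 38.2 |

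One dropped eye adds 13/42 − 13/43 = 0.7 points in control, or 26/42 − 26/43 = 1.4 points in the visco arm. If all dropped eyes were in Cohort 1, eight per arm would be 8/21 = 38% of that cohort's eyes in the arm, so that row is a high assumption.

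**Illustration of on-drug scoring.** If five medicated eyes in each arm were all at least 20% down on drug, the rates would be 18/43 = 41.9% and 31/43 = 72.1%. This is the most that five eyes could add.

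**Is dropping neutral?** If the dropped eyes would respond off drug at the same rate as the rest, yes. With 13/38 = 34.2% among assessed eyes and the same rate in the other five, the whole arm is also at 34.2%, and scoring the five as failures (30.2%) would be too low. There is some reason to doubt equality. Protocol 7.4.2 allows medication after the first month at IOP above 21 mmHg, and entry IOP is 21 to 36 mmHg (Protocol 6.1). Since 0.8 × 26.25 = 21.0, an eye with baseline at or below 26.25 mmHg that exceeded 21 mmHg was less than 20% down at that moment. Eyes with a higher baseline are not covered: at 36 mmHg the 20% line is 0.8 × 36 = 28.8 mmHg.

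**The case against.** The strongest reply is that the SAP already fails these eyes. The outcome is defined as response off medication, the rate is the share of eyes meeting that outcome, and the denominator asks only for non-missing pressures. A medicated eye seen at Month 12 has a recorded pressure, so it stays in and fails. This reading is open. It means that a reader who infers that the SAP definitely removes these eyes, or that the primary result is inflated, goes further than the documents allow. What stands is that the text does not choose between the readings, and the washout note points away from this one at Month 12.

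Other replies carry weight:

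- Parts of Section 5 are redacted, including all of 5.2, and a rule may sit there.
- The 26.25 mmHg argument concerns pressure when medication was started, not off-drug pressure at Month 12. Protocol 7.4.1 also allows medication in the first month, partly at the investigator's discretion. The protocol text available is version D, while the SAP is based on version F.
- Failing an eye because its protocol version did not require washout is debatable. Available-case reporting agrees with Protocol 8.3, which uses the number available for analysis. The available-case result therefore belongs beside any failure rule.
- The visible SAP gives per-arm rates with exact intervals and no between-arm test, so the gaps in the table illustrate a contrast that the visible text does not formally test.
- Month 12 medication use is a secondary endpoint, and individual pressures and medication counts are listed, so affected eyes can be found afterwards. That helps a later re-analysis but does not fix the primary rule in advance.

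**Conclusion.** The point holds as a gap in the visible rule and should be fixed. SAP 5.1 does not apply the endpoint's own medication condition to an eye on medication with no washed-out IOP. Dropping such eyes, or scoring them on drug, can overstate an arm's response rate. With three to eight assumed drops per arm, the rates rise by 2.3 to 6.9 points in control (32.5 − 30.2; 37.1 − 30.2) and by 4.5 to 13.8 points in the visco arm (65.0 − 60.5; 74.3 − 60.5).

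The real number of eyes and their split by arm are not in the documents. It would be tempting to infer that the treatment effect is exaggerated, but the documents do not support this: the gap widens with equal drops, narrows to 26.3 points when only control eyes are dropped, and widens to 38.2 when only visco eyes are. The problem falls mainly on Cohort 1, though not only there, since a required washout can still be missed. Pooling the cohorts in the tables would hide it. Confidence is medium because of the redactions and the competing reading.

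**What to change.** State in SAP 5.1, in substance:

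> IOP response uses only unmedicated IOP; for an eye on IOP-lowering medication at Month 12 this is the Month 12 Washout value. As an exception to Section 3.1, an eye on IOP-lowering medication at a visit with no washed-out IOP for that visit stays in the denominator as a non-responder.

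Report, by arm and cohort, how many Month 12 eyes were unmedicated, washed out, and medicated without washout.

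Add two sensitivity analyses, overall and by cohort:

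- **(a) Available-case:** drop medicated eyes without washout.
- **(b) Strict:** count every eye on medication at Month 12 as a non-responder. The primary rule lets a washed-out eye respond but fails a medicated eye for which no washout was required; (b) puts both cohorts under one rule.

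If a redacted section already contains the rule, a cross-reference in 5.1 is enough.

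The cost is SAP wording and table programming. The SAP already plans to list each subject's 12-month IOP on and off medication and the number of medications. The downside is that reported rates may be somewhat lower, and some eyes that would have responded off drug count as failures in the primary analysis. Analysis (b) is stricter still, because it also fails eyes that responded after washout.

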5.3 Statistical Methods for Efficacy Analyses

The primary efficacy endpoint, the achievement of a 20% decrease in IOP relative to baseline in the absence of IOP lowering medications up to 12 months post-operatively will be summarized at each post-operative visit by the number and percent of subjects having IOP response and the corresponding 95% confidence interval (CI) based on the exact binomial distribution.

[figure not shown]
Secondary efficacy endpoints describing proportions meeting given criteria will be summarized at each post-operative visit by the number and percentage of responses and the corresponding 95% CI based on the exact binomial distribution. While descriptive statistics for all continuous parameters for the actual values and change from baseline, including the 95% CI of the actual/observed results (based on a *t*-distribution) and change (based on a paired *t*-distribution), will be provided for each protocol specified visit, the 12 month visit is of most interest.

All efficacy analysis summaries will be produced using the FAS set.

Document: TDOC-0053376 Version: 2.0; Most-Recent; Effective; CURRENT

Status: Effective

Document: TDOC-0053376 Version: 2.0; Most-Recent; Effective; CURRENT

Status: Effective

6 Safety Analysis Strategy

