## 8. STATISTICAL METHODS

#### 8.1 Sample Size

The primary effectiveness endpoint is the outcome of  $\geq 20\%$  decrease in IOP from baseline without IOP lowering medications up to 12 months post-operatively (IOP response). The proportion of eyes meeting the effectiveness outcome, IOP response rate, will be assessed at 12 months. A sample of at least 101 eyes will be enrolled across the two groups (CyPass only control and CyPass + Healon 5 dose selected) with an estimated 86 eyes completing their month 12 visit. Assuming a 30% success rate for the control eyes and a 60% success rate for the visco-assisted eyes, 80% power can be achieved with 43 eyes per arm using a two-tailed alpha of 0.05.

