## 8.3 Efficacy and Safety Analyses

The primary effectiveness endpoint, the achievement of a 20% decrease in IOP relative to baseline in the absence of IOP lowering medications will be summarized at each postoperative visit by the number available for analysis (N), the proportion meeting success criteria, and the 95% confidence interval (CI).

Secondary endpoints describing proportions meeting given criteria will be summarized at each postoperative visit by N, percentage and 95% CI. Continuous endpoints, IOP, mmHg decrease

in IOP and % decrease in IOP will be summarized by N, mean, standard deviation median, minimum and maximum. For continuous change measures, the 95% CI of that change will also be provided.

The safety profile of the CyPass device will be based on intraoperative and postoperative adverse event rates, slit lamp biomicroscopy and fundus examination. All subjects who undergo CyPass implantation surgery will be included in the safety analysis. The incidence of adverse events will be summarized by N, percentage, and CI.

An adverse event (AE) is any untoward medical occurrence, unintended disease or injury or any untoward clinical sign occurring in a study subject, whether or not related to the CyPass Micro-Stent. All AEs in the study eye must be reported on the appropriate CRF. Each AE must be graded by degree of harm to the subject (note grading scale below), as well as by the relationship to study device or implantation procedure.

AEs should be graded as follows:

- Mild: Discomfort noticed but no disruption of normal daily activity
- Moderate: Discomfort sufficient to reduce or affect normal daily activity
- Severe: Incapacitating with inability to work or perform normal daily activity

Ocular conditions or diseases that are chronic but stable and do not render the subject ineligible for the study should be recorded under the subject's ocular history. Changes in the chronic condition or disease consistent with natural progression are not considered AEs.

AEs associated with glaucoma surgical procedures that might reasonably be expected to occur in this study are listed below. These anticipated AEs include, but are not limited to:

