6.3.4 Intraocular Pressure

Intraocular pressure (IOP) measurements will be recorded in mmHg and reported up to one decimal place. IOP measurements will be summarized relative to both medicated and unmedicated baseline assessments compared to postoperative visits as follows. For medicated baseline IOP, descriptive summaries of observed values, as well as change and percent change from medicated baseline (Baseline1) values will be presented at each postoperative assessment visit compared to medicated baseline. Similarly, descriptive

Document: TDOC-0053376 Version: 2.0; Most-Recent; Effective; CURRENT

Status: Effective

summaries of observed values, as well as change and percent change from unmedicated baseline (Baseline2) values will be presented at each postoperative assessment visit compared to unmedicated baseline.

Further, IOP measurements over time at the Screening, Baseline, 1 Mo, 3 Mos, 6 Mos, 12 Mos, and 12 Mos unmedicated assessments will be presented graphically using side-by-side box plots to compare results between the CyPass alone and CyPass with 60 µL groups.

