6.3.11 Device Deficiencies

The applicable definition of a device deficiency is in the study protocol. A listing of all device deficiencies, as recorded on the Device Deficiency Log, will be provided.

7 Sample Size and Power Calculations

The primary effectiveness endpoint is the outcome of \geq 20% decrease in IOP from baseline without IOP lowering medications up to 12 months post-operatively (IOP response). The proportion of eyes meeting the effectiveness outcome, IOP response rate, will be assessed at 12 months. A sample of at least 101 eyes will be enrolled across the two groups (CyPass only control and CyPass + Healon 5 dose selected) with an estimated 86 eyes completing their month 12 visit. Assuming a 30% success rate for the control eyes and a 60% success rate for the visco-assisted eyes, 80% power can be achieved with 43 eyes per arm using a two-tailed alpha of 0.05 that is based on the Likelihood Ratio Chi-square test for two proportions. It is

Document: TDOC-0053376 Version: 2.0; Most-Recent; Effective; CURRENT

Status: Effective

estimated that approximately 10% of those receiving the CyPass Micro-Stent may be lost to follow-up.

Document: TDOC-0053376 Version: 2.0; Most-Recent; Effective; CURRENT

Status: Effective

Date/Time (mm/dd/yyyy GMT):	Signed by:	Justification:
05/29/2017 11:06:02		
05/30/2017 18:23:03		
06/05/2017 20:12:51

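### Does the plan fail to commit to the two-arm comparison of Month 12 response for which the trial is sized?

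*SAP*

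**What the plan says.** **Sizing.** Protocol 8.1 states that "80% power can be achieved with 43 eyes per arm using a two-tailed alpha of 0.05". SAP section 7 repeats this, gives the rates ("Assuming a 30% success rate for the control eyes and a 60% success rate for the visco-assisted eyes") and adds the test: the calculation is "based on the Likelihood Ratio Chi-square test for two proportions". Both sections name the two groups and place the assessment at 12 months.

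**Analysis set.** SAP 2.1 makes the full analysis set, as randomised, the primary set for efficacy.

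**Efficacy methods that can be read.** SAP 5.3 summarises the primary endpoint at each visit "by the number and percent of subjects having IOP response and the corresponding 95% confidence interval (CI) based on the exact binomial distribution". Secondary proportions also get exact binomial intervals, and continuous measures get t and paired-t intervals. Protocol 8.3 likewise reports a count, a proportion and a 95% interval. SAP section 3 describes the analyses as summaries, with change from baseline assessed within each treatment. On layout, SAP 3.1 says: "Summary tables will be presented by treatment and overall, as appropriate, for both phases/cohorts combined".

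**Between-arm display that can be read.** Apart from section 7, the only sentence that sets the two arms against each other is in the safety part. SAP 6.3.4 plans "side-by-side box plots to compare results between the CyPass alone and CyPass with" 60 µl.

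**The concern.** Read in order, the plan seems to promise one thing and deliver another. Power is a property of a test between two arms. An exact binomial interval for one arm is a one-sample statement, and the stated 80% does not attach to it.

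The comparison matters here because both arms receive the stent. A response rate within one arm mixes the effect of the stent with that of the viscoelastic; only the randomised difference isolates the viscoelastic. The trial is also unmasked (SAP 1.4), and Cohort 1 results were reviewed before the expansion. If the test and the effect estimate were truly left open, they could be chosen with the data in view, and the sample-size section would justify an analysis to which nobody had committed.

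Per-arm intervals would be a poor substitute. If the arms were judged by whether the two exact intervals fail to overlap, power at 43 per arm would be only about 45%.

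**Working it through.** **1. The plan's own figure.** Inputs from SAP section 7: rates 0.30 and 0.60, two-sided alpha 0.05, likelihood ratio chi-square test. Equal arms are assumed, so the pooled rate is 0.45. The noncentrality with n eyes per arm is

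λ = 2n[f(0.30) + f(0.60)], where f(p) = p ln(p/0.45) + (1 − p) ln((1 − p)/0.55).

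- f(0.30) = 0.3 ln(0.3/0.45) + 0.7 ln(0.7/0.55) = 0.0472
- f(0.60) = 0.6 ln(0.6/0.45) + 0.4 ln(0.4/0.55) = 0.0452
- Sum = 0.0924

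At n = 42, λ = 84 × 0.0924 = 7.76 and power is 79.6%. At n = 43, λ = 86 × 0.0924 = 7.95 and power is 80.5%. So 43 is the smallest number per arm that reaches 80% with exactly the test that section 7 names. The usual pooled-variance formula gives 42. The likelihood ratio test was therefore really the basis of the calculation.

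**2. What the readable text fixes for the comparison.**

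| Element | Stated as | Place |
|---|---|---|
| Groups | CyPass alone; CyPass plus selected Healon 5 dose | SAP 7, Protocol 8.1 |
| Selected dose | 60 µl | SAP 1.2 |
| Outcome | IOP fall of at least 20% without medication | SAP 5.1, SAP 7 |
| Time point | 12 months | SAP 5.1, SAP 7 |
| Level | two-sided 0.05 | SAP 7, Protocol 8.1 |
| Test | likelihood ratio chi-square | SAP 7 |
| Analysis set | full analysis set, as randomised | SAP 2.1 |

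Two things cannot be read: a sentence in the methods section that this test will be run, and a named interval for the difference.

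**3. Where the readable text stops.** The SAP contents list 5.1 at page 13, an unlabelled entry at page 15, 5.3 at page 16, a second unlabelled entry at page 16, and section 6 at page 18. Section 5.3 thus has pages 16 and 17 available, but only two short paragraphs and one sentence of it can be read. A block is not shown directly after the primary-endpoint sentence. At the end of 5.3 two page headers follow each other with nothing between them, as a fully blanked page would leave. Section 5.2 is absent altogether. In the parallel safety chapter, 6.1 holds endpoints, 6.2 hypotheses and 6.3 methods. With 5.1 on endpoints and 5.3 on methods, 5.2 is plausibly the efficacy hypotheses; that is an inference. SAP 6.2 disclaims formal hypotheses for safety only.

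**4. How much an open choice of test would matter.** Exact power at 43 per arm is the sum, over all pairs (x, y) for which the test rejects, of Bin(x; 43, 0.30) × Bin(y; 43, 0.60).

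| Test | Exact power |
|---|---|
| Likelihood ratio | 81.0% |
| Pearson | 81.0% |
| Fisher | 73.7% |

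Likelihood ratio and Fisher reach different verdicts in 7.3% of such trials. One example is 13/43 versus 22/43, with p = 0.047 and p = 0.078. Near the design rates (13/43 versus 26/43) the two exact intervals, 17.2–46.1% and 44.4–75.0%, overlap slightly, although the difference is 13/43 = 30.2 points and the likelihood ratio p is 0.0045. These figures are correct, but they measure a move from the named test to Fisher's test, which appears nowhere in either document.

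**The case for a change.** The strongest argument for the concern does not depend on the blanked pages. Protocol 8.3 states the primary analysis in a complete sentence with no apparent cut, and that sentence is purely descriptive. SAP section 3 uses the same language of summaries and within-treatment change. Section 7 says what the power rests on; it does not say that the test will be performed. On this view the blanks are a coincidence and the plan really contains no comparison.

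Part of this stands. The readable methods text is descriptive, and the words of section 7 alone are a basis for sizing and not an instruction to analyse. It cannot be shown that the withheld text contains the test.

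The converse cannot be shown either, and the concern needs the converse. The protocol supplied is Version D, while the SAP was written to Version F, so Protocol 8.3 does not settle what the later plan contains. Protocol numbering also runs from 8.1 to 8.3, and whether an 8.2 existed cannot be told. A general opening sentence in SAP section 3 does not rule out a specific test two sections later. And if the trial was meant to be descriptive, the power statement would be a planning figure, and the contrast between likelihood ratio and Fisher would have no object.

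**Conclusion.** The concern does not hold as a finding about the plan. It infers an omission from a chapter whose relevant parts are blanked in the public copy, and text withheld in this way cannot be counted as missing. The fear that the analysis could be chosen freely after the data are seen is also too strong: groups, outcome, time point, level, test and analysis set all stand in readable text, and a switch to another test would be a visible departure from SAP section 7.

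No size can be attached to an error that is not shown. The sizing is sound (80.5% power at 43 per arm by the likelihood ratio approximation, 81.0% by exact enumeration). The gap of 7.3 percentage points to Fisher's test describes a change that no passage proposes.

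This conclusion rests on the gaps in SAP 5.2 and 5.3 being withheld text and not sections that never existed; the blank contents entries and the empty page support that. If the complete SAP proved to contain no between-arm analysis, the point would have to be reopened. On the public record it is a request for confirmation.
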